## STUDY PROTOCOL AND STATISTICAL ANALYSIS PLAN

**Document date:** 20.01.2020

**Title study:** Cellular Proliferation, Dermal Repair, and Microbiological Effectiveness of Ultrasound-Assisted Wound Debridement (UAW) Versus Standard Wound Treatment in Complicated Diabetic Foot Ulcers (DFU): An Open-Label Randomized Controlled Trial.

An open-label randomized and controlled parallel clinical trial was performed involving 51 outpatients with complicated DFU that were admitted to specialized diabetic foot unit between November 2017 to December 2019. This study protocol received full approval from the local Ethics Committee of the Hospital Clínico San Carlos, Madrid, Spain (C.P.-C.I. 16/484-P). All patients provided written informed consent before inclusion. The present study was registered retrospectively in ClinicalTrial.gov (Registration no.: NCT04633642).

### 2. Methods

#### 2.1. Trial Design

An open-label randomized and controlled parallel clinical trial was performed involving 51 outpatients with complicated DFU that were admitted to specialized diabetic foot unit between November 2017 to December 2019.

#### 2.2. Participant

We enrolled patients in which the following inclusion criteria were implemented:

- Male and female patients over 18 years old

Type 1 or type 2 diabetes with levels of HbA1c  $\leq 85.8$  mmol/mol (10%) within 30 days of the beginning of the study, based on a previous international, multicenter, randomized controlled trial [11]

- Wound stages IB, IIB, ID, and IID according to the University of Texas Diabetic Wound Classification [12]
- Wound duration of 1–24 months
- Wound size among 1–30 cm^2 after debridement

- Diabetic foot ulcers showing mild or moderate infection, according to the criteria of the European Wound Management Association (EWMA) [13] and the Infectious Disease Society of America Guidelines [14]
- Ankle-brachial index (ABI)  $> 0.9$  or  $ABI \leq 0.9$  and ankle systolic blood pressure (ASBP)  $\leq 70$  mmHg, or toe systolic blood pressure (TSBP)  $50$  mmHg. In patients with medial arterial calcification (ABI  $> 1.4$ ) we considered Peripheral Arterial Disease (PAD) a toe-brachial index (TBI)  $< 0.7$  [15,16]

We considered exclusion criteria:

- Chronic kidney disease (glomerular filtration rate  $< 60$  mL/min per 1.73 m^2 during at least three months) or dialysis [17]
- Non-treated osteomyelitis
- Necrotizing soft tissue infections
- Critical limb ischemia patients with ABI  $< 0.5$  and ASBP  $< 70$  mmHg or  $< 50$  mmHg [15,16]

Life expectancy  $< 6$  months due to malignant DFU

- Pregnancy and lactation
- Patients diagnosed with human immunodeficiency virus (HIV) or hepatitis
- Patients showing local or systemic conditions that could impair tissue regeneration.

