### 2.3. DFU Assessment

A senior clinician in the management of diabetic foot ([name]) always carried the baseline assessment of patients' DFU. Sensorimotor neuropathy of DFUs was diagnosed using a biothesiometer (both from Novalab Iberica, Madrid, Spain) and Semmes-Weinstein 5.07/10g monofilament. Patients who did not feel one of the two tests were diagnosed with neuropathy [18,19].

Brachial and ankle systolic pressure were evaluated using a manual 8MHz Doppler (Doppler II, Huntleigh Healthcare Ltd., Cardi, UK). Toe systolic pressure was taken via digital plethysmography (Systoe, Atys Medical, Madrid, Spain). Wound tissue oxygen levels were measured using transcutaneous oxygen readings (Radiometer Medical, Brønshøj, Denmark).

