### 2.5. Outcome Measures

**2.5.1. Main Outcome Measure: Cellular Proliferation Analysis of Wound Tissue Samples.** The same senior clinician interpreted all samples to evaluate the cellular proliferation. The microvascular structure of CD31, an endothelial marker, was subjected to immunohistochemical analysis and quantification to understand the effects of debridement on neo-angiogenesis, [22]. Sections of tissue sample were immunohistochemically stained with the CD31 marker. Light microscopy was used to count the number of microvessels/endothelial cells in a standardized grid, with the results expressed as microvessel density (Leica DMD 800 morphometric system). Microvessel density was scored in proportion to the following scale: 0 (absent), 1 (low, at least one microvessel), 2 (moderate) and 3 (more than two microvessels).

To differentiate collagen content from other components, such as muscle fibrin and erythrocytes, in tissue samples we used Massons's trichome staining. Collagen content was scored according to the following scale: 0 (absent), 1 (mild), 2 (moderate) and 3 (severe) [23].

Actin staining was used to evaluate the presence of myofibroblasts involved in wound healing. These cells increase in number during wound healing. The number of stained cells was semi-quantitatively analyzed using a 0–3 scaling score (0 = no myofibroblasts, 1 = myofibroblasts in low quantities, 2 = myofibroblasts in moderate quantities, 3 = myofibroblasts in high quantities).

**2.5.2. Secondary Outcome Measure: Microbiological Analysis of Wound Tissue Samples** Specimens of wound tissue were homogenized in 0.5 mL volumes of sterile phosphate buffered saline (PBS, Sigma Aldrich, St Louis, MO). After mechanical homogenization, the specimens were seeded in Columbia agar (BD, Sparks, MD), MacConkey agar (BD), Sabouraud dextrose agar (BD) and Columbia

agar supplemented with nalidixic acid and colistin (BD) using a spiral plater Workstation (Don Whitley Scientific, Shipley, UK). Quantitative and qualitative microbiological analyses were performed after incubation of plates at 37 °C for 24 h. Isolated microorganisms were identified by standard methods and susceptibility testing was performed in accordance with Clinical and Laboratory Standards by the disk diffusion method [24]. The results were expressed as CFU per gram of tissue (CFU/g) and the limit of detection was 10 colony-forming units (CFU).

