## 2.8. Randomization

A computer-generated random number table was used to carry out the randomization of the patients into the two groups by an investigator who was unaware of the identity of the participants.

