## 2.10. Statistical analysis

Data were analyzed, based upon an intention-to-treat analysis, using the software package SPSS for iOS version 21.0 (SPSS, Inc. Chicago, IL, USA). Kolmogorov-Smirnov test was used to verify the assumption of normality of all continuous variables. Chi-square test was performed to calculate differences between groups and, if applicable, Fisher's exact test for categorical variables. Student's t-test and Mann-Whitney U test were performed for normally and abnormally distributed quantitative variables, respectively. Graphics to evaluate the differences among decrease in bacterial load and cellular proliferation between groups were done using GraphPad® for Mac OS.

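### Section 2.10 compares the arms without the ischaemic/non-ischaemic split or the week-0 biopsy score, giving up precision and protection against chance imbalance

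*Combined protocol and SAP*

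**What the plan says.** All references are to the combined protocol and SAP.

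- **Eligibility (2.2).** The accepted ulcers are "Wound stages IB, IIB, ID, and IID according to the University of Texas Diabetic Wound Classification [12". The vascular criterion admits ABI above 0.9 and, with a pressure condition, ABI at or below 0.9. For calcified arteries it adds that "we considered Peripheral Arterial Disease (PAD) a toe-brachial index (TBI" falls below 0.7. Critical limb ischaemia is excluded.
- **Baseline perfusion (2.3).** "Brachial and ankle systolic pressure were evaluated using a manual 8MHz Doppler", toe pressure was taken by plethysmography, and "Wound tissue oxygen levels were measured using transcutaneous oxygen readings".
- **Main outcome (2.5.1).** CD31 staining comes first of three markers, with "immunohistochemical analysis and quantification to understand the effects of debridement on neo-angiogenesis" as its stated purpose. "Light microscopy was used to count the number of microvessels/endothelial cells in a standardized grid", and the result is scored 0 to 3. Collagen and myofibroblasts are also scored 0 to 3.
- **Biopsies (2.4.2).** One at week 0 and one at week 6, each after a debridement session.
- **Randomisation (2.8).** "A computer-generated random number table was used to carry out the randomization of the patients into the two groups". Strata, blocks and minimisation are not mentioned.
- **Analysis (2.10).** Chi-square or Fisher's exact test for categorical variables; otherwise "Student's t-test and Mann-Whitney U test were performed for normally and abnormally distributed quantitative variables, respectively". There is no stratified test, covariate model or baseline adjustment. Decreases in bacterial load and cellular proliferation are mentioned only in connection with graphics.

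**The concern.** The entry criteria create two perfusion groups, and the first marker of the main outcome is a vessel count. Perfusion is therefore a plausible predictor of that marker, and the trial holds the data to account for it. The same is true of the week-0 score, the most direct predictor of the week-6 score. The plan uses neither.

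Two things are at stake. First, variance between stages, and between patients at week 0, stays in the error term, so the trial has less power than its data allow. Second, if the arms happen to differ in stage mix, a reader cannot tell from the planned tests how much of an observed difference reflects that mix.

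**Working it through.** **The plan's own figure.** The only related figure is the sample size in 2.7: 51 patients, power 0.80, alpha 0.05, a 37% difference. Endpoint, control rate, SD and sidedness are not given, so it cannot be uniquely reproduced. A two-sided two-proportion formula with a 37-point difference and control rates of 0 to 0.60 gives totals of 34 to 56 without continuity correction. For example, 0.15 vs 0.52 gives 25 per arm, or 51 in total at a 27:24 ratio. So 51 is attainable but not verifiable. Nothing below depends on it except the arm sizes.

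**Inputs.** From 2.7: 24 and 27 patients. Assumed, because the documents are silent: stage D share p, stage effect d on a 0–3 score, and within-stage SD 0.8. The documents do not define the stage letters. I take B as infected and D as infected and ischaemic; the ABI criterion shows a perfusion mix independently of that reading.

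**Step 1: chance of imbalance under simple randomisation.** SD of the difference in stage D share = sqrt(p(1−p)(1/24 + 1/27)), and 1/24 + 1/27 = 0.0787.

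- p = 0.5: sqrt(0.25 × 0.0787) = 0.140
- p = 0.3: sqrt(0.21 × 0.0787) = 0.129

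The exact hypergeometric chance of a difference of 20 points or more is 8.1% with 10 of 51 in stage D, 12.3% with 15, 16.1% with 20 and 16.4% with 26. A binomial calculation gives 15.8% at p = 0.5 and 11.1% at p = 0.3.

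**Step 2: size of the shift.** Shift = imbalance × d. At 20 points it is 0.20 × 0.6 = 0.12 for d = 0.6, and 0.20 × 1.0 = 0.20 for d = 1.0. At p = 0.5 the unadjusted SEs are sqrt((0.64 + 0.25 × 0.36) × 0.0787) = 0.240 and sqrt((0.64 + 0.25) × 0.0787) = 0.265. The shifts are thus about 0.5 and 0.8 SE.

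**Step 3: effect of adjustment on the SE.** Ratio adjusted/unadjusted = sqrt[0.64 × (1 + 1/47) / (0.64 + p(1−p)d²)]. The factor 1 + 1/47 is the expected cost of one covariate, with 51 − 1 − 3 = 47.

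| d | p = 0.3 | p = 0.5 |
|---|---|---|
| 0.2 | 1.004 | 1.003 |
| 0.4 | 0.985 | 0.980 |
| 0.6 | 0.956 | 0.946 |
| 1.0 | 0.877 | 0.857 |

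At p = 0.2 and d = 0.2 the ratio is sqrt(0.64 × 1.0213 / 0.6464) = 1.006. If stage has no effect at all, it is sqrt(1.0213) = 1.011. These are linear-model figures and apply only approximately to an ordinal model or a rank test.

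**Step 4: simulation** (8,000 trials per setting, p = 0.5, within-stage SD 0.75). With a true arm effect of 0.6 points, adjustment raises power from 76% to 80% if d = 0.5, and from 63% to 79% if d = 1.0. With no true effect, the unadjusted test rejects in 5.0% (d = 0.5) and 4.9% (d = 1.0) of all trials. Among trials imbalanced by at least 20 points it rejects in 8.3% and 13.5%.

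**The case against.** A reader might infer that the missing stratification biases the result, or that stage imbalance invalidates the planned tests. The documents do not support that. Chance imbalance is already allowed for in the unadjusted test's standard error, and Step 4 shows the 5% error rate holding overall. The 8.3% and 13.5% describe only the minority of trials with a large imbalance, and nothing in the documents shows that this trial is one of them. Section 2.8 is also silent on blocks and strata rather than stating that there were none.

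The size of the gain is assumed. No stage share, stage effect or SD is given, and 2.5.1 does not say that the CD31 score depends on limb perfusion. Excluding critical limb ischaemia, and conditions that could impair regeneration, narrows the contrast between stages. This stands, and it is why the range has to include a small loss.

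A stable difference between stages would already appear in the week-0 score, so adjusting for that score would remove much of what stage explains. This also stands. It makes the week-0 score the more direct omission, and Step 3 overstates what stage adds once that score is in the model.

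Depth, duration, area and infection severity are plausible predictors too. Singling out perfusion is a judgement, resting on its link to a vessel count and on its being built into eligibility. Finally, an analysis added after enrolment in an open-label trial is a late choice. That calls for labelling, not for leaving it out.

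**Conclusion.** The point holds as one of efficiency and robustness, not validity. The plan has, or should be able to derive, a perfusion split and a week-0 score, and commits to neither. For an assumed stage D share of 20% to 50%, the chance of a 20-point imbalance is about 8% to 16%. For assumed stage effects of 0.2 to 1.0 points, within-stage SD 0.8 and a share of 30% to 50%, adjusting for stage moves the SE by between a loss of about 0.4% and a gain of about 14%. The loss is about 1% if stage has no effect. The gain from the week-0 score is not quantified, because the documents give no correlation between the two biopsies.

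That stage is on file for every patient is inferred from its being an entry criterion; 2.3 lists the pressures and oxygen readings but not stage.

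**What to change.** In section 2.10:

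1. Report stage B and D counts by arm.
2. Compare the week-6 0–3 scores by ordinal regression on arm, week-0 score and stage B vs D, or by a van Elteren test stratified by stage.
3. For continuous outcomes, use a model with arm, baseline value and stage.
4. Label these analyses as specified after enrolment and report the unadjusted test beside each.

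The week-0 biopsy follows a debridement session, so that score may not be strictly pre-treatment. Section 2.10 should say so. The van Elteren version does not use the score and is a useful check.

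The cost is SAP wording, one degree of freedom per term, and the weaker standing of a late-specified analysis. If neither term predicts the outcome, two terms cost about 2% in SE: sqrt(1 + 2/46) = 1.022, with 51 − 2 − 3 = 46. No new data are needed if stage was recorded. No change to 2.8 is proposed: enrolment ended in December 2019 and the document is dated 20.01.2020.

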### 2.3. DFU Assessment

A senior clinician in the management of diabetic foot ([name]) always carried the baseline assessment of patients' DFU. Sensorimotor neuropathy of DFUs was diagnosed using a biothesiometer (both from Novalab Iberica, Madrid, Spain) and Semmes-Weinstein 5.07/10g monofilament. Patients who did not feel one of the two tests were diagnosed with neuropathy [18,19].

Brachial and ankle systolic pressure were evaluated using a manual 8MHz Doppler (Doppler II, Huntleigh Healthcare Ltd., Cardi, UK). Toe systolic pressure was taken via digital plethysmography (Systoe, Atys Medical, Madrid, Spain). Wound tissue oxygen levels were measured using transcutaneous oxygen readings (Radiometer Medical, Brønshøj, Denmark).

## 2.4. Intervention

2.4.1. DFU Debridement and Wound Management Patients were randomly assigned to receive either surgical debridement or UAW debridement every week during a six-week treatment period. All debridement procedures were performed by the same surgeon ([name]), who is a specialist in the field of diabetic foot surgery with more than 21 years of experience.

Surgical debridement involved removal of all necrotic and devitalized tissue that was incompatible with healing, as well as surrounding callus.

UAW debridement was performed using an UAW SONOCA 185 device (Söring GmbH, Quickborn, Germany) by a senior clinician ([name]) with more than three years of experience applying this type of debridement. The UAW device is equipped with three UAW instruments with different sonotrode shapes and generates an ultrasound low frequency of 25 kHz. The choice of sonotrode depends on ulcer depth (ranges from superficial to deep). The UAW device piezoelectrically transforms the electrical energy delivered from the UAW device into mechanical oscillations in the sonotrode tip. In the majority of diabetic foot ulcers in the UAW group, a two-minute treatment with 40% intensity was made by holding the sonotrode in contact mode, holding it perpendicular to the wound bed and moving it across in an up-and-down pattern. For diabetic foot ulcers measuring  $> 15 \text{ cm}^2$ , the debridement treatment was increased to three minutes. In addition to UAW debridement, a scalpel was used for careful tissue removal, but only in cases where periwound tissue exhibited calluses or maceration.

Between debridement sessions, sterile saline was used to clean all wounds prior to evaluation and all patients received standard of care for their diabetic foot ulcers, which consisted of moist wound dressings for wound management and proper off-loading (a removable walker cast based on the functioning and ambulatory status of the patient) as per the International Working Group of the Diabetic Foot guidelines [1,20]. When necessary, patients with moderate infections took empirical antibiotics during the treatment period, based on IDSA guideline recommendations [14], until the results from deep tissue culture were available [21]. After we received tissue culture results, we adjusted the antibiotic therapy to target the bacteria that were isolated during tissue culture.

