#### 2.4.2. Analysis of Tissue Samples

Soft tissue punch biopsies (3 mm) were taken after wound debridement sessions at week zero (day 0) and week six (day 42). After tissue collection, samples were immediately transported to the laboratory for cellular proliferation and microbiological analyses.

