## 2.9. Blinding

None of the participants, care providers and outcome adjudicators were blinded to the interventions after assignment.

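### Bacterial load is compared without entry infection severity, and no planned output shows whether discretionary, unblinded antibiotic use differed between arms

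*Combined protocol and SAP*

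**What the plan says.** Eligibility in section 2.2 covers "Diabetic foot ulcers showing mild or moderate infection", so severity is assessed at entry. Section 2.4.1 describes antibiotics for one of these two groups: "When necessary, patients with moderate infections took empirical antibiotics during the treatment period". Once cultures were back, "we adjusted the antibiotic therapy to target the bacteria that were isolated during tissue culture". The text places this under standard care for all patients and draws no distinction between arms.

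Section 2.5.2 is headed "Secondary Outcome Measure: Microbiological Analysis of Wound Tissue Samples" and reports CFU per gram of tissue, with a detection limit of 10 CFU. Section 2.4.2 times the biopsies at day 0 and day 42, both after debridement.

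On allocation, section 2.8 says "A computer-generated random number table was used to carry out the randomization of the patients into the two groups" and mentions no stratification. Section 2.9 says "None of the participants, care providers and outcome adjudicators were blinded to the interventions after assignment". Section 2.10 specifies an intention-to-treat analysis using Student's t-test or Mann-Whitney for quantitative variables and chi-square or Fisher's exact test for categorical ones. No section plans to report infection severity or antibiotic use by arm, or to use either in the analysis.

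**The concern.** Antibiotics can be expected to act on the quantity being measured. Who receives them depends on a factor known at entry, and whether and which ones are given is settled after randomisation by clinicians who know the arm. Two separate problems follow.

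- **Precision.** If moderate cases are treated and mild ones mostly are not, the antibiotic effect spreads the CFU/g values within each arm. A two-group test carries that spread as noise, although part of it is predictable from severity.
- **Interpretation.** If unblinded decisions led to more antibiotic use in one arm, the contrast would combine debridement with the additional antibiotics. No planned table would reveal this.

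Microbiological effectiveness is in the study title, so a secondary outcome carries a prominent claim.

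**Working it through.** **Inputs from the documents.** 24 surgical and 27 UAW patients, 51 in all (section 2.7); antibiotics described for moderate cases only (2.4.1); unadjusted tests (2.10). The power statement in 2.7 names no endpoint and gives no SD for CFU/g, so there is no planned figure for bacterial load to reproduce.

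**Assumptions, because the documents give no values.** Half the patients moderate; residual SD 1.5 log10; UAW effect 1.2 log10; antibiotic effect *b* of 0.5 to 3 log10; a fraction *f* of moderate cases treated, equal in both arms unless stated.

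**Step 1: chance imbalance in severity.** The SE of the arm difference in the moderate share is sqrt(0.25 × (1/24 + 1/27)) = 0.140, so 95% of differences lie within 1.96 × 0.140, about ±27 points. With all moderate cases treated, this moves the contrast by an SD of 0.14 × *b*: 0.14, 0.28 or 0.42 log10 at *b* = 1, 2 or 3. This is sampling error that the t-test's SE already contains. Simulated with no UAW effect and the same antibiotic rule in both arms, the unadjusted test has a type I error of 0.048 to 0.052 and a mean bias below 0.01 log10.

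**Step 2: precision.** With share treated q = 0.5*f*, the within-arm variance is 1.5² + *b*² q(1 − q). Once severity is in the model, the average residual variance is 1.5² + 0.5 *b*² *f*(1 − *f*). The SE of the contrast is SD × sqrt(1/24 + 1/27) = SD × 0.2805. Worked at *b* = 2:

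- *f* = 1, unadjusted: variance 2.25 + 4 × 0.25 = 3.25, SD 1.80, 1.2/(1.80 × 0.2805) = 2.37, power about Φ(2.37 − 1.96) = 66%.
- *f* = 1, adjusted: SD 1.5, 1.2/(1.5 × 0.2805) = 2.85, power about Φ(0.89) = 81%.
- *f* = 0.5, unadjusted: variance 2.25 + 4 × 0.1875 = 3.00, SD 1.73, ratio 2.47, power about 69%.
- *f* = 0.5, adjusted: variance 2.25 + 0.5 × 4 × 0.25 = 2.75, SD 1.66, ratio 2.58, power about 73%.

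Simulation with t-based tests gives values one to three points lower (unadjusted → adjusted):

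| Antibiotic effect (log10) | All moderate cases treated | 80% treated | Half treated |
|---|---|---|---|
| 0.5 | 78 → 78% | – | – |
| 1 | 75 → 78% | 76 → 78% | 77 → 77% |
| 2 | 64 → 79% | 64 → 74% | 67 → 70% |
| 3 | 50 → 79% | 53 → 68% | 58 → 63% |

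**Step 3: differing use by arm.** Suppose 90% of moderate cases are treated in one arm and 60% in the other, with no UAW effect. The contrast shifts by 0.5 × (0.9 − 0.6) × *b* = 0.15, 0.30 or 0.45 log10 at *b* = 1, 2 or 3. At *b* = 2 the simulated type I error is 9.4% unadjusted and 9.8% with severity in the model. The covariate does not help, because the difference arises after randomisation among patients of the same severity.

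**The case against.** A reader might infer that, because severity is ignored, the trial cannot separate debridement from antibiotics. The documents do not support that. Severity precedes randomisation and is balanced in expectation, and 2.4.1 gives one antibiotic rule for everyone. The unadjusted contrast therefore validly compares the two debridement methods on top of that care, as step 1 confirms. Nor does 2.10 credit the fall within one arm to debridement; it refers to differences between groups. All of this stands.

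It is also fair to say that the power gain rests on inputs the documents do not give, that it shrinks to between 0 and 5 points if only half of moderate cases are treated, and that severity adjustment does nothing about differing use. No passage shows that use did differ by arm. The outcome is secondary.

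These objections limit the size of the point but do not remove it. Adjusting for a factor already assessed at entry is close to free. Without exposure by arm, no reader can tell whether step 3 applies.

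**Conclusion.** The point holds in a limited form. The bacterial-load comparison is valid as a test of debridement added to standard care, but it is less precise than it could be. The plan also contains nothing that would show whether a CFU/g difference reflects debridement alone.

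Under the stated assumptions, the precision at stake ranges from nothing (antibiotic effect 0.5 log10) to about 30 points of power (3 log10, all moderate cases treated), and is 0 to 5 points at 1 to 3 log10 if half are treated. The shift from differing use would be 0.15 to 0.45 log10 at 90% versus 60%, but that split is illustrative.

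Two further inferences should be avoided. Severity adjustment is not a correction for antibiotic use. The mild group cannot be taken as free of antibiotics, because 2.4.1 does not say that mild cases received none.

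**What to change.** In section 2.10:

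1. Compare log10 CFU/g in a linear model with arm and entry infection severity (mild v moderate), or use a rank test stratified by severity. State the value assigned to non-detects on the per-gram scale, since 2.5.2 gives the detection limit in CFU. Say that the adjustment is for precision and does not correct for differing antibiotic use. Do not add antibiotic use as a covariate, because it is determined after randomisation.
2. Tabulate entry severity and antibiotic exposure (agent, start, duration, changes) by arm up to the day-42 biopsy, where the records allow. If exposure differs, word the microbiological conclusion as debridement plus the antibiotics given. Show the mild-infection subgroup descriptively only; under the half-and-half assumption it holds about 12 v 13 patients.

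The cost is one degree of freedom and one table. Severity was assessed for eligibility; the documents do not say how antibiotic use was recorded, so the table depends on what can be retrieved. Stratified randomisation is no longer open, as the document is dated January 2020 and admissions ran to December 2019. No change to antibiotic care is proposed.
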